2.6 Rationale for Cross-Over Design (Effective with Amendment 5A)

For patients who progress on Arm C (nivolumab monotherapy), evolving clinical options include simple 'continuing beyond progression', change to anti-VEGF TKI-based therapy, or the addition of anti-VEGF TKI-based therapy. The concept of continuing on PD1 inhibitor-based therapy beyond progressive disease, which at times occurs in the setting of mixed responses, has been formally investigated in multiple cancers including renal cell carcinoma.⁵⁶⁻⁵⁹ Available data suggest that continuing such therapy is both safe, and at times, efficacious^{57, 58} with potential improvements noted in overall survival.⁵⁹ That said, either switching to or adding an anti-VEGF TKI-based therapy can be effective in some RCC variants.⁶⁰ Considering existing standards in management of RCC and the goals of this trial, cross-over from Arm C (nivolumab monotherapy) to Arm A (combination nivolumab/axitinib therapy) will be permitted for patients on Arm C at first disease progression. Data that results from such cross-over will not impact the primary aim of the study, but will contribute to our understanding of tRCC patient clinical tolerance and response to such therapies, survival outcomes, and pharmacokinetics of axitinib in pediatric patients treated with combination therapy.

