4.1 Overview of Treatment Plan

Prior to Amendment 2A, the study was a randomized three-arm phase 2 study evaluating the clinical benefit of axitinib, nivolumab, and their use in combination for the treatment of tRCC.

As of Amendment 2A, Arm B (axitinib alone) is permanently closed to accrual, and prospective patients will be randomly assigned to one of the following arms:

Arm A: Axitinib + Nivolumab

Arm C: Nivolumab

As of Amendment 5A, patients who are initially randomized to Arm C (nivolumab alone) and experience progressive disease prior to Cycle 22 will be permitted to crossover to Arm A (axitinib + nivolumab). For patients who crossover to Arm A, they are to continue on their current nivolumab schedule and start axitinib as soon as it is made available. NOTE: Patients must use the NCI supplied drug. Commercially supplied axitinib is not allowed.

Axitinib will be administered at a starting dose of 5 mg PO BID for patients \geq 18 years of age, and at 2.4 mg/m²/dose (maximum of 5 mg/dose) PO BID for patients $<$ 18 years of age. See [Appendix IV](#) for axitinib dosing nomogram. Individual patient dose titration of axitinib (escalation from starting dose) is permitted on protocol therapy, at the discretion of the treating physician. Refer to [Section 4.3.3](#) or [4.4.3](#) for dose titration criteria.

Nivolumab will be given at either 240 mg IV every 2 weeks or 480 mg IV every 4 weeks for patients \geq 18 years of age, and at 3 mg/kg IV (maximum of 240 mg/dose) every 2 weeks for patients $<$ 18 years of age. Pre-medication is not required as infusion reactions are rare, but anaphylactic precautions should be observed during each infusion of nivolumab. If \geq Grade 2 infusion reaction occurs, the infusion should be stopped and supportive care given as per institutional guidelines. See [Section 5.3](#) for management and dose modification guidelines for infusion reactions. Investigators are advised to monitor for fever, chills, shakes, itching, rash, hypertension or hypotension, or difficulty breathing during and immediately after administration of nivolumab.

Combination therapy will be given with agents at full single agent doses as above.

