Each cycle of therapy will be 4 weeks. Tumor disease evaluation will occur after Cycles 2, 4, 6, 9, 12, and then every 4 cycles thereafter, or at any time clinical progression is suspected. If pseudoprogression is suspected (until any degree of response is observed), disease evaluation must occur after every cycle ([Section 10.2.1](#)). Absent disease

progression or unacceptable toxicity, patients may continue on protocol therapy for up to 2 years duration or completion of 26 cycles, whichever comes first. Disease evaluations (including imaging) will continue during follow-up according to the schedule outlined in [Section 7.2](#).

For patients who progress on Arm C prior to Cycle 22, cross-over to Arm A is permitted. Patients should resume Arm A therapy as soon as PD is identified. Nivolumab should continue uninterrupted according to the previously established schedule for that patient (either every 2 or 4 weeks). Axitinib should be added as soon as it becomes available from NCI and the patient has recovered from any relevant toxicity. Subsequent disease evaluations should occur as above timed from the first cycle of combination therapy. The first cycle of combination therapy after cross-over will be defined as the cycle for which > 14 days of axitinib is given, with Day 1 of Cycle 1 after cross-over defined as the day of first nivolumab dose during that cycle after axitinib is started or on the day axitinib is started if given concurrently. **NOTE:** The total protocol therapy received on AREN1721 (whether delivered on Arm A, Arm C, or Arm C+A) is not to exceed 26 cycles or 2 years, whichever comes first.

NOTE:

- Patients who have not had cytoreductive nephrectomy prior to trial enrollment but who elect to have cytoreductive nephrectomy during therapy may remain on protocol therapy.
- Cytoreductive therapy is not permitted in the first 12 weeks after starting protocol therapy.
- Axitinib must be held for 7 days before and after surgery. See [Section 13.1.2](#) for more details.

For COG Supportive Care Guidelines see:

<https://childrensoncologygroup.org/index.php/cog-supportive-care-guidelines>.

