4.5.3 Treatment Details – Arm C: Nivolumab

Each cycle lasts 28 days (4 weeks). Absent disease progression or unacceptable toxicity, patients may continue on protocol therapy for up to 2 years duration or completion of 26 cycles, whichever comes first.

Criteria to start each cycle: ANC \geq 1000/ μ L, platelet count \geq 75,000/ μ L without transfusion support. See [Section 5.0](#) for other requirements related to any ongoing toxicities.

Nivolumab: IV over 30 minutes or per institutional guidelines

Age	Dose and Days
\geq 18 years old	Either 240 mg/dose on Days 1 and 15 OR 480 mg/dose on Day 1 only
< 18 years old	3 mg/kg/dose (maximum 240 mg/dose) on Days 1 and 15

The risk of infusion reactions with nivolumab is low and no pre-medications are required. Monitoring for infusion reactions should be per institutional guidelines. Please refer to [Section 5.3.2](#) for suggested infusion reaction management guidelines.

Nivolumab will be distributed by the Division of Cancer Treatment and Diagnosis (DCTD), NCI. Do not use commercial supply.

See [Section 5.0](#) for Dose Modifications based on Toxicities.

Following completion of a cycle, begin next cycle on Day 29 or when criteria to begin cycle are met, whichever occurs later.

Patients on Arm C that meet protocol defined criteria of disease progression prior to Cycle 22 of therapy, may cross-over and receive Arm A (combination) therapy. Total therapy received on study AREN1721, either on Arm A, Arm C, or for patients that cross-over, is not to exceed 26 cycles total or 2 years, whichever comes first.

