8.0 CRITERIA FOR REMOVAL FROM PROTOCOL THERAPY AND OFF STUDY CRITERIA

8.1 Criteria for Removal from Protocol Therapy

- a) For Arms A and C, progressive disease of $\geq 40\%$ increase in total tumor burden from baseline or nadir at any time during protocol therapy (see [Section 10.2](#)) (see exception below).
- b) For Arms A and C, progressive disease of $\geq 20\%$ increase in total tumor burden from baseline or nadir that occurs > 12 weeks after start of protocol therapy, except if a patient met the criteria for pseudoprogression in the first 12 weeks and the total tumor burden has subsequently stabilized or decreased with no additional growth (see [Section 10.2](#)) (see exception below).
- c) For Arm B, progressive disease of $\geq 20\%$ increase from baseline or nadir in total tumor burden at any time during protocol therapy (see [Section 10.2](#)).
- d) Response followed by $\geq 20\%$ increase in total tumor burden from the nadir at any time during protocol therapy (see [Section 10.2.5.1](#)) (see exception below).
- e) Appearance of one or more new lesions or unequivocal progression of non-target lesions (see [Section 10.2.5.2](#)) and refer to [Section 10.2.1](#) for exceptions within the first 12 weeks of therapy (see exception below).
- f) Resection of any malignant lesion within the first 12 weeks of protocol therapy (see [Section 13.1.8.1](#)).
- g) Resection of any lesion that is increasing in size at any time while on protocol therapy (see [Section 13.1.8.2](#)).
- h) Completion of planned therapy.
- i) Unacceptable toxicity due to protocol therapy (see [Section 5.0](#)).
- j) Refusal of further protocol therapy by patient/parent/guardian.
- k) Physician determines it is in patient's best interest.
- l) Development of a second malignancy.
- m) Pregnancy.
- n) Repeat eligibility studies (if required) are outside the parameters required for eligibility (see [Section 3.2](#)).

Exception: Patients on Arm C who meet the protocol defined criteria of disease progression prior to Cycle 22 of therapy, may cross-over and receive the remainder of their protocol therapy per Arm A. For those patients who cross-over, the total protocol therapy received on AREN1721 is not to exceed 26 cycles or 2 years, whichever comes first.

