9.5 Monitoring Boundary for Dose-Limiting Toxicities

Definitions of DLTs provided in ADVL1315 (for axitinib related DLTs) and ADVL1412 (for PD1-targeting immune checkpoint DLTs) will be used ([Section 5.1](#)). DLTs in each arm will be monitored at least weekly to ensure there is no excess toxicity, specifically. No

more than 3 patients (in the first 10 patients treated) experiencing protocol-defined DLTs during the first cycle (4 weeks) of treatment, and no more than 30% of patients experiencing protocol-defined DLTs during the first cycle (4 weeks) of treatment thereafter. Excess toxicities in the combination arm will lead to temporary suspension of accrual so discontinuation or dose reduction may be considered via a formal amendment.

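### The Section 9.5 toxicity pause stops accrual but not cross-over starts on axitinib + nivolumab, and it is unclear whether DLTs after cross-over count towards it

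*Combined protocol and SAP*

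**What the plan says.** **The boundary (Section 9.5).** DLTs are monitored by arm, at least weekly. At most 3 of the first 10 treated patients may have a first-cycle DLT. After that the limit is "no more than 30% of patients experiencing protocol-defined DLTs during the first cycle (4 weeks) of treatment thereafter". The consequence is that "Excess toxicities in the combination arm will lead to temporary suspension of accrual", while stopping the combination or lowering its dose is taken up by amendment. Section 9.5 does not mention cross-over.

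**The cross-over (Amendment 5A).** Under Section 4.1, Arm C patients who "experience progressive disease prior to Cycle 22 will be permitted to crossover to Arm A". Section 4.5.3 says that they "may cross-over and receive Arm A (combination) therapy". The exception in Section 8.1 says that they "may cross-over and receive the remainder of their protocol therapy per Arm A". On timing, Section 4.1 says: "Axitinib should be added as soon as it becomes available from NCI and the patient has recovered from any relevant toxicity". None of these places makes a cross-over start depend on the Section 9.5 boundary or on a pause.

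**Scan timing.** Cycles last 4 weeks, and "Tumor disease evaluation will occur after Cycles 2, 4, 6, 9, 12, and then every 4 cycles thereafter", with extra imaging if clinical progression is suspected.

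**Other oversight.** Section 5.1 asks that the Study Chair be told of any DLT. Section 11.10 makes all DLTs routinely reportable. Section 9.3 reports adverse events with cross-over as a third group. Section 12.2 provides for DSMC review.

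**The concern.** A toxicity pause exists to stop new exposure to a regimen that looks too toxic until someone has reviewed it. Here there are two ways onto the regimen and the pause closes one. A site following the text would stop randomizing, yet could start its next progressing Arm C patient on the same two drugs.

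The count raises a related doubt. The window is the first 4 weeks of treatment, and for an Arm C patient those weeks are nivolumab alone. Early toxicity after axitinib is added may therefore not feed the check that triggers the pause.

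The population makes this more than a drafting matter. Section 2.3 states that no data on this combination exist in children, and cross-over is open to patients under 18 (Section 15.1 requires their PK samples).

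**Working it through.** Section 9.5 states no power or error rate to reproduce. The check is a comparison of the texts, then a rough size.

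**1. Window against cross-over date**
- The window closes on day 28.
- The first scheduled scan follows Cycle 2: 2 × 28 = day 56.
- A cross-over prompted by a scheduled scan therefore starts at least 56 − 28 = 28 days after the window has closed.
- The exception is an unscheduled scan in Cycle 1. With exponential PFS and a median of 5 or 8.2 months, the share progressing by day 28 is 1 − 0.5^((28/30.44)/median) = 12% or 7%. Fewer would be detected and on axitinib by then. *Normally closes* is the right strength.

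**2. After accrual ends**
- Remaining accrual is estimated at 14 months (Section 9.1). After that there is no accrual to suspend.
- Cross-over stays open for 21 cycles: 21 × 28 = 588 days = 84 weeks, about 19 months from each Arm C start.

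**3. Chance that Arm A trips the first-10 limit**

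P(4 or more DLTs of 10), binomial:

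| True 4-week DLT rate | Probability |
|---|---|
| 20% | 12% |
| 30% | 35% |
| 40% | 62% |

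**4. New cross-over starts during a pause**

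Assumptions:
- One Arm C entry per month at mid-month (half of the 2 per month in Section 9.1), with n entries when the limit trips.
- Exponential PFS with hazard h = ln 2 / median. The medians of 5 and 8.2 months are taken from the anti-VEGF figures for tRCC in Section 2.1.1, because no nivolumab figure for tRCC is given.
- Every PFS event crosses over.

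Patients still progression-free at month n: F = Σ exp(−h(n − i + 0.5)), for i = 1 to n. Starts in a pause of k months: F × (1 − exp(−hk)).

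For k = 3, the factor 1 − exp(−3h) is 0.340 (median 5) or 0.224 (median 8.2).

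| Arm C entries n | F (5 / 8.2) | Already progressed, n − F | Starts in 3 months |
|---|---|---|---|
| 5 | 3.60 / 4.08 | 1.40 / 0.92 | 1.2 / 0.9 |
| 7 | 4.48 / 5.28 | 2.52 / 1.72 | 1.5 / 1.2 |
| 10 | 5.41 / 6.75 | 4.59 / 3.25 | 1.8 / 1.5 |
| 14 | 6.17 / 8.20 | 7.83 / 5.80 | 2.1 / 1.8 |

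The row n = 10 treats the trial as empty at re-opening, which it is not. The table in Section 9.2 gives an average N of 24 to 26 after 9 to 10 months. At 2 per month that is 18 to 20 new patients, so about 5 to 6 were already enrolled. With about 3 of them in Arm A, that arm reaches 10 near month 7, and n = 7 is the closer row. The roughly 3 earlier Arm C patients would add some starts.

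Deaths, refusals and the pseudoprogression allowance of Section 10.2.1 all reduce these figures. A fair summary is about 1 to 2 starts in 3 months.

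**The case against.** **The pause is only a first step.** Section 9.5 ties it to an amendment on the combination itself, which could cover cross-over. That is fair while accrual is open: the gap then lasts only as long as the pause. It does not help during the pause, or after accrual ends.

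**Arm can be read broadly.** Cross-over patients are said to move to Arm A, Section 9.3 treats them as a third arm for adverse events, and Section 4.1 defines a first combination cycle for them. This stands in part, so the counting point is an ambiguity and not a proven omission. But where the protocol restarts a clock it says so, for imaging and for PK. The existing definition would also fit badly: it needs more than 14 days of axitinib, so a patient stopped by a DLT on day 10 might not qualify.

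**Other controls exist.** Cross-over is permitted, not required. Axitinib must come from NCI, which is also the IND sponsor. DLTs go to the Study Chair, and the DSMC may recommend changes. All true, but none is a prespecified hold on cross-over starts.

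**Stronger readings that the documents do not support.** A reader might infer that cross-over patients are unmonitored; the controls above rule that out. A reader might also infer that cross-over patients dilute the Arm A DLT rate by entering its denominator without countable events; nothing in the plan directs such a count.

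**Conclusion.** The point holds. On the action, the text is plain: the one automatic step stops accrual, and nothing links cross-over starts to it. On the count, the window normally closes at least 4 weeks before axitinib is added, and whether later DLTs count is left open.

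The size is modest and rough: about 1 to 2 new cross-over starts in a 3-month pause. It is conditional on a pause, and rests on borrowed PFS medians, an assumed entry rate and an uncertain number of patients already enrolled. In a trial with a target of 28 patients it is still worth closing.

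A reader might infer that the cross-over group needs its own formal stopping limit. The numbers do not make that necessary. With 5 cross-over patients, a limit of 3 in 10 would trip with probability 3% at a true DLT rate of 30% and 9% at 40%. Extending the hold carries most of the protection.

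**What to change.** **Main change.** In Section 9.5, suspend accrual and all new starts on axitinib + nivolumab, including by cross-over, until review is complete. Add a matching sentence to the cross-over exception in Section 8.1. The sponsor must also decide what happens to a patient who progresses on Arm C during the pause. If nivolumab alone may continue meanwhile, Sections 8.1 and 10.2.1 must say so, because both otherwise require removal. Section 2.6 gives supporting background on treatment beyond progression ("Available data suggest that continuing such therapy is both safe, and at times, efficacious"), but it is rationale and not permission. Without such text, removal under Section 8.1 applies.

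**Secondary change.** In the weekly DLT review, add a separate cross-over row with its own denominator, counting Section 5.1 DLTs in the 28 days from the first axitinib dose. A fixed 28 days matches the length of the existing window.

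**Optional.** A formal limit for that row. With the rule checked after each patient and 14 patients in Arm A, adding 5 to 10 cross-over patients as a second, independent group raises the chance of some pause from 25% to 26–34% at a true DLT rate of 20%, and from 58% to 59–73% at 30%.

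**Cost.** A few sentences in Sections 9.5 and 8.1, one table row, and edits to Section 10.2.1 if treatment while waiting is allowed. DLTs are already collected (Section 11.10). The primary PFS comparison is unaffected, since outcomes after cross-over are not counted in it (Section 9.3). The real downside is that a progressing Arm C patient may wait for or miss cross-over during a pause.

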9.6 Gender and Minority Accrual Estimates

The gender and minority distribution of the study population (up to ceiling of 40 patients) is expected to be as follows:

DOMESTIC PLANNED ENROLLMENT REPORT						
Racial Categories	Ethnic Categories				Total	
	Not Hispanic or Latino		Hispanic or Latino			
	Female	Male	Female	Male		
American Indian/ Alaska Native	0	0	0	0	0	
Asian	0	1	0	0	1	
Native Hawaiian or Other Pacific Islander	0	0	0	0	0	
Black or African American	6	7	0	0	13	
White	11	11	2	2	26	
More Than One Race	0	0	0	0	0	
Total	17	19	2	2	40	

This distribution was derived from AREN03B2.

10.0 EVALUATION CRITERIA

10.1 Common Terminology Criteria for Adverse Events (CTCAE)

This study will utilize version 5.0 of the CTCAE of the National Cancer Institute (NCI) for toxicity and performance reporting. A copy of the CTCAE version 5.0 can be downloaded from the CTEP website (http://ctep.cancer.gov/protocolDevelopment/electronic_applications/ctc.htm). Additionally, toxicities are to be reported on the appropriate case report forms.

Please note: 'CTCAE v5.0' is understood to represent the most current version of CTCAE v5.0 as referenced on the CTEP website.

10.2 Response Criteria for Patients with Solid Tumors

Response and progression will be evaluated in this study using the new international criteria proposed by the revised Response Evaluation Criteria in Solid Tumors (RECIST) guideline (version 1.1), with the exceptions described in [Section 10.2.1](#) below to account for possible "pseudoprogression" during treatment with immunotherapy (iRECIST).⁶² The major change in iRECIST is the concept of allowing for the possibility of "pseudoprogression", which occurs when standard RECIST v1.1 progression (> 20% increase in tumor burden from baseline) during the first 12 weeks of treatment is followed at the next assessment by tumor shrinkage.⁶³ Consistent with iRECIST and this definition of pseudoprogression, in the current study, further progression above and beyond the usual 20% threshold will be required to meet the definition of progressive disease for any patient who has not yet completed 12 weeks of protocol therapy.

Following baseline evaluation and treatment initiation, patients should be re-evaluated for lesion response or progression after Cycles 2, 4, 6, 9, 12 and then every 4 cycles thereafter with additional imaging required (1) after every cycle following possible pseudoprogression until subsequent response is documented, and (2) at any time clinical progression is expected. During follow-up, repeat imaging evaluations should occur according to the schedule described in [Section 7.2](#). Confirmatory scans should also be obtained 6-8 weeks (not less than 4 weeks) following initial documentation of objective response.

At each imaging timepoint, the largest diameter (unidimensional measurement) of each target, non-target, or new lesion and the shortest diameter (axis) for each malignant lymph node should be recorded. Any lesions that were surgically resected since the last imaging assessment should be explicitly noted, along with the date and rationale for removal, and an indication of whether the lesion had been increasing in size at the time of surgical removal.

IMPORTANT NOTE: *All calculations of percentage change in total tumor burden to assess response or progression should fully exclude from consideration any malignant lesions that were surgically resected at any time prior to the most recent response assessment.*

10.2.1 Exceptions for Possible Delayed Response ('Pseudoprogression') – only applicable for patients on Arms A and C

Patients in whom the magnitude of increase in tumor size is $\geq 20\%$ but $< 40\%$ from baseline may remain on protocol therapy **for up to 12 weeks after start of protocol therapy** if all of the following criteria are met, to allow for the possibility of pseudoprogression followed by a later tumor response (which may occur during treatment with immunotherapy):

- In the judgment of the treating clinician, the patient does not show evidence for rapid disease progression or the patient has shown evidence for clinical benefit.
- There is no decrease in performance status.
- The patient is tolerating the study drug and there has been no DLT (see [Section 5.1](#)).
- Continued treatment with nivolumab alone or in combination with axitinib will not delay an imminent intervention required to prevent a serious complications (e.g. CNS metastases which require radiation therapy or surgery).

For response assessments occurring during the first 12 weeks on protocol therapy, new lesions with a longest diameter of $< 10\text{ mm}$ (or newly noted lymph nodes with short axis $< 15\text{ mm}$) should not be counted toward the total tumor burden. Only new lesions with a longest diameter $\geq 10\text{ mm}$ (or lymph nodes with short axis $\geq 15\text{ mm}$) should be included in the total tumor burden and assessments of percentage change from baseline or nadir.

For patients who remain on protocol therapy despite an increase in tumor burden $\geq 20\%$ (possible pseudoprogression) during the first 12 weeks, imaging to include target lesions must occur every cycle, and the same radiographic and clinical criteria must be met in order to remain on protocol therapy. If tumor burden subsequently diminishes to $< 20\%$ increase from baseline or nadir, the patient may

be followed according to the standard protocol guidelines which will involve less frequent imaging. The decision to continue treatment beyond radiographic evidence for disease progression ($\geq 20\%$ increase in tumor burden) may be discussed with the study PI and should be documented in the study record.

If at the Week 12 assessment the total tumor burden has not yet diminished to $< 20\%$ increase from baseline or nadir, a patient may stay on protocol therapy so long as tumor shrinkage/stabilization continues to occur. If at any point after Week 12 the total tumor burden increases *and* is $\geq 20\%$ from baseline or nadir, this will be defined as progressive disease and the patient must be removed from protocol therapy.

Patients whose best response in the first 12 weeks is pseudoprogression, but who subsequently come off protocol therapy prior to any further assessment, will be considered as having progressive disease. This will include patients who are removed from protocol therapy due to resection of tumor lesions that are increasing in size (see [Section 13.1.8.2](#)).

Note: An increase in tumor size of $\geq 40\%$ at any time will be considered true progression and will result in removal from protocol therapy.

